6 ENDPOINTS AND COVARIATES

All primary and secondary endpoints are based on scales, either assessed by the physician or the patient. Baseline is defined as day 1, the respective time windows for post-baseline visits are given in Table 2.

6.1 EFFICACY/EFFECTIVENESS ENDPOINT(S)

Effectiveness endpoints comprise of all primary and secondary endpoints, i.e. effectiveness, and quality parameters assessed by the physicians and the patients.

Primary endpoint analysis

Variable	Role	Data source(s)	Operational definition
EASI	Primary outcome variable	Case records	Percentage of patients with 75% reduction from baseline in EASI at month 3
IGA	Primary outcome variable	Case records	Percentage of patients with IGA score 0 or 1 at month 3

Secondary endpoint analysis

Variable	Role	Data source(s)	Operational definition
SCORAD	Secondary outcome variable	Case records	Summary statistics (n, mean, median, standard deviation, minimum and maximum) of the total score and SCORAD-A at each point in time, respectively as well as the respective percentage change to baseline
EASI	Secondary outcome variable	Case records	 Percentage of patients with 75% reduction from baseline in EASI irrespective of the point in time Percentage of patients with 90% reduction from baseline in EASI irrespective of the point in time Summary statistics (n, mean, median, standard deviation, minimum and maximum) of the score at each point in time as well as the respective percentage change to baseline
IGA	Secondary outcome variable	Case records	 Percentage of patients with IGA score 0 or 1 irrespective of the point in time Percentage of patients with IGA score 0 or 1 and a reduction from baseline of ≥2 points irrespective of the point in time Summary statistics (n, mean, median, standard deviation, minimum and maximum) of the score at each point in time as well as the respective percentage change to baseline ((score at respective visit – score at baseline)/score at baseline*100)

Pruritus- NRS	Secondary outcome variable	Case records	Percentage of patients achieving at least 4 points improvement of Pruritus NRS from baseline Summary statistics (n, mean, median, standard deviation, minimum and maximum) of the score at each point in time as well as the percentage change to baseline Percentage of patients with Pruritus NRS ≤1
PP- NRS	Secondary outcome variable	Case records	 Percentage of patients achieving at least 4 points improvement of PP NRS from baseline Summary statistics (n, mean, median, standard deviation, minimum and maximum) of the score at each point in time as well as the percentage change to baseline Percentage of patients with PP NRS ≤1
DLQI	Secondary outcome variable	Case records	 Percentage of patients achieving at least 4 points improvement of DLQI from baseline Summary statistics (n, mean, median, standard deviation, minimum and maximum) of the score at each point in time as well as the percentage change to baseline Percentage of patients with DLQI ≤1
POEM	Secondary outcome variable	Case records	Summary statistics (n, mean, median, standard deviation, minimum and maximum) of the score at each point in time as well as the percentage change to baseline
MOS-Sleep scale	Secondary outcome variable	Case records	Summary statistics (n, mean, median, standard deviation, minimum and maximum) of the

scales at each point in time as well as the percentage change to baseline Summary statistics (n, mean, median, standard deviation, minimum and maximum) of the Patient single items and the total score at Case records Benefit Secondary outcome variable each appropriate point in time as Index well as the percentage change to visit 2 (about one months after baseline) Patient Expectation As measured by PBI questionaire s on and (refer to line above; expectation Satisfaction PBI at baseline, satisfaction PBI at Secondary outcome variable Case records with all points in time after baseline) abrocitinib treatment Summary statistics (n, mean, median, standard deviation. minimum and maximum) of the EQ-5D-5L VAS and EQ-5D index score at Secondary outcome variable Case records each point in time as well as the percentage change to baseline Summary statistics (n, mean, median, standard deviation, minimum and maximum) of the **HADS** anxiety score and depression score Secondary outcome variable Case records at each point in time, respectively as well as the percentage change to baseline Number of Date of first topical treatment – date days with of last topical treatment + 1 topical treatment Secondary outcome variable Case records Summary statistics (n. mean. median, standard deviation, use (TCS, TCI) minimum and maximum) Date of first emollients use – date of last emollients use + 1 Number of days with emollients Secondary outcome variable Case records Summary statistics (n, mean, use median, standard deviation, minimum and maximum)

Analysis of questionnaires

Questionnaire	Analysis
SCORAD	Scoring Atopic dermatitis: validated scoring index for AD for severity, combining A: extent (0-100), B: severity (0-18) and C: subjective symptoms (0-20) based on itching and sleep deprivation,
	each scored (0-10). The SCORAD for an individual is calculated using the formula $A/5 + 7B/2 + C$ (may range from 0 to 103).
EASI	Eczema Area and Severity Index assesses both clinical signs of AD as well as extent of disease; scores can range from 0 to 72, with higher scores representing greater severity of AD. For "head and neck", "trunk", "upper extremities" and "lower extremities" the extent of eczema is assessed
	by an area score between 0 and 6, respectively. For each area the severity of "erythema", "edema/papulation", "excoriation" and "lichenification" is scored 0 to 3, respectively. The scores
	for the signs are added for each area and multiplied by the respective arera score. The EASI for an individual is calculated as weighted sum: 0.1 x score for head/neck $+ 0.3 \text{ x}$ score for trunk $+ 0.2 \text{ x}$ score for upper extremities $+ 0.4 \text{ x}$ score for lower extremities.
IGA	Investigators Global Assessment: assesses the severity of AD (excluding scalp, palms and soles) on a 5-point scale from 0 (clear) to 4 (severe) from the investigator's perspective.
Pruritus-NRS	The NRS is comprised of one item and represents the numbers 0 ("no itch") to 10 ("worst imaginable itch"). Subjects are asked to rate the intensity of their average pruritus using this scale.
Peak-Pruritus- NRS	Numeric rating scale: evaluates itching in the last 24 hours from no itching [0] to worst possible itching [10].
POEM	Patient-oriented Eczema Measure: patient-reported measure that assesses AD symptoms. The patient himself evaluates the frequency of occurrence and severity of 7 symptoms (such as itching
	and burning of the skin) within the last week, each according to a 5-point Likert scale from 0 ("at no day") to 4 ("at all days"). The severity is summed over the symptoms. The maximum POEM score is 28 points.
	If one question is missing it is scored with 0 and the scores are summed as described before. If two or more questions are not answered the questionnaire is not scored.
	If two or more questions are not answered the questionnaire is not scored. If two or more response options are selected, the response option with the highest score should be recorded.
DLQI	The DLQI is a 10-item patient-reported measure that rates how much a patient's skin problems have affected their life over the last week assigned to the following 6 dimensions: symptoms, daily life, leisure/sport, work/school, social life/relationship and abrocitinib treatment. For each
	question, 0 to 3 points are given, whereby 3 points indicate the greatest possible impairment of the QoL in the queried area. The sum of scores ranges from 0 to 30, with higher scores indicating greater impairment of quality of life. If one question is unanswered it is scored with 0. If more than one question is not answered the score cannot be determined.
	(https://www.cardiff.ac.uk/medicine/resources/quality-of-life-questionnaires/dermatology-life-quality-index)
MOS	The Medical Outcomes Study Sleep Scale (MOS-Sleep) includes 12 items assessing sleep disturbance (questions 1, 3 (R-reversed), 7 (R) and 8(R)), sleep adequacy (questions 4 (R) and 12 (R)), somnolence (questions 6 (R), 9(R) and 11 (R)), quantity of sleep (question 2), snoring (question 10 (R)), and awakening short of breath or with a headache (question 5 (R)) whereat question 1 scores from 1 (0-15 min) to 5 (>60 min) and questions 3 to 12 from 1 (all of the time) to
	5 (none of the time). 1 is recoded to 0, 2 to 25, 3 to 50, 4 to 75 and 5 to 100. If the answers have to be reversed 1 is recoded to 100, 2 to 75, 3 to 50, 4 to 25 and 5 to 0. The scores represent the average for all items in the scale that were answered, i.e. missing data are not taken into account.
PBI	Measurement of patient defined treatment benefits according to German and international standards, contains two one-sided questionnaires which are to be completed by the patient before and after receiving a treatment. A total of 25 possible treatment goals are evaluated on an
	importance scale from 0 ("not at all") to 5 ("very"). "does not apply to me" will be coded as "0". The analysis will include: a) means and standard deviations of all items ("does not apply to me" is
	coded as 0 for this single-item analysis of the PBI) b) for each item the percentage of the response "does not apply to me" c) for each item the percentage of responses with high agreement (quite or very) d) percentage of missing values The weighted index value, the actual "Patient Benefit Index"
	(PBI), is calculated by multiplying the achieved benefits (respective PBI after baseline) with the importance of the respective needs prior to therapy (PBI at baseline), dividing these products by the sum of all importance items (PBI at baseline), and summing them up for all items. The total PBI score ranges from 0 (no benefit) to 5 (maximal benefit).

EQ-5D-5L	Generic instrument for measuring quality of life, including health benefits and health status on a visual analogue scale (VAS), using the five dimensions (mobility, self-care, usual activities, pain/discomfort, anxiety/depression). The health status is given as a sequence of the five diemnsions. Missing values are coded as "9". However the EQ-5D index score can only be determined according to the EQ-5D-5L German values if all 5 health dimensions have been specified.
HADS	The Hospital Anxiety and Depression Scale is a 14-item measure that identifies anxiety (7 items) and depression (7 items) among adults who are physically ill with lower scores indicating lower levels of anxiety and depression. Scoring for each item ranges from 0 to 3, with 3 denoting highest anxiety or depression level. For both subscales the score is derived by summing up the respective 7 items.

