9.1.1. Endpoints

Primary Endpoints:

- a. Response based on achieving the **IGA** of clear (0) or almost clear (1) (on a 5-point scale) at month 3.
- b. Response based on achieving the **EASI-75** at month 3.

Secondary Endpoints:

Physician's global assessment of efficacy parameters (assessed at all visits [except for month 3 for a. and b.]):

- a. Response based on achieving the **IGA** of clear (0) or almost clear (1) (on a 5-point scale).
- b. Percentage of patients with EASI-75 response compared to baseline.
- c. Response based on achieving the EASI-90.
- d. Response based on achieving the **IGA** of clear (0) or almost clear (1) and a reduction from baseline of ≥ 2 points.
- e. Percentage change of **IGA** compared to baseline.
- f. Percentage change of **SCORAD** compared to baseline.
- g. Absolute **EASI** values over time.
- h. Percentage change of EASI compared to baseline.
- i. Absolute change of **IGA** compared to baseline.

Patient's assessment of efficacy and quality parameters (assessed at all visits):

- a. Response based on achieving at least 4 points improvement of Pruritus **NRS** from baseline.
- b. Change of Peak-Pruritus NRS over time.
- c. Change of **POEM** from baseline.
- d. Change of MOS from baseline.
- e. Change of DLQI from baseline.

- f. Change of HADS from baseline.
- g. Change of EuroQol five-dimensional-five level (EQ-5D-5L) from baseline.
- h. Patient's satisfaction with treatment measured by PBI.
- i. Patient's expectation of treatment measured as PBI at baseline.
- j. Number of days with topical-treatment use (TCS, TCI).
- k. Number of days with emollients use.

Explorative Endpoints:

Treatment characteristics (assessed at all visits):

- a. Concomitant treatments.
- b. Tolerability of abrocitinib and reasons for discontinuation.
- c. Dosage of abrocitinib.
- d. Compliance with abrocitinib treatment.

Patient characteristics assessed at baseline visit only (except for c., f., g., and h. with additional assessment at subsequent visits):

- a. Demographic data of patient (age, sex, weight, occupation, alcohol/smoking, family history).
- b. Clinical history of AD treatment before non-interventional study start.

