2 INTERIM ANALYSES

Two interim analyses are planned for this study. Table 3 shows the planned analyses schedule. Results of earlier interim analyses will be updated in each later analysis.

Table 3. Content of Interim analysis

Table 3 Content of Interim Analysis

Analysis	Year	Population cut-off	New Content
Interim analysis 1 (IA1)	Not applicable – see population cut-off	When approximately 15 % of patients completed Visit 1	Baseline characteristics, explorative endpoints as well as usage of abrocitinib and effectiveness at visit 2.
Interim analysis 2 (IA2)	Not applicable – see population cut-off	When approximately 40 % of patients completed Visit 4	Baseline characteristics, explorative endpoints as well as usage of abrocitinib and effectiveness at each available timepoint.
Final analysis	2028	All patients	Patient characteristics, usage and effectiveness, anything not yet analyzed.

Two interim analyses will be carried out. The first interim analysis (IA) will be conducted when approximately 15 % of the planned number of patients have reached their V1 (baseline) visit. The IA1 interim analysis will consider explorative endpoints with focus on baseline characteristics, transition to abrocitinib treatment as well as usage of abrocitinib and effectiveness at visit 2 respectively.

The interim analysis will be repeated (IA2) when approximately 40 % of patients completed visit 4. This interim analysis will consider the same aspects as IA1 and effectiveness at every other available timepoint.

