5.3 OTHER ANALYSIS SET

The modified Full Analysis Set (mFAS) consists of all patients who met the eligibility criteria, received at least one dose of abrocitinib and had at least one post-baseline visit. This population will be used for analysis of primary and secondary endpoints, if $\geq 10\%$ of the FAS is omitted.

The Per Protocol Set (PP) consists of all patients who met the eligibility criteria, received at least one dose of abrocitinib and completed all visits, irrespective of the time-window.

This population will be used for analysis of primary and secondary endpoints, if $\geq 10\%$ of the mFAS is omitted.

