8.2.3 Summary of Analyses

Outcome	Analysis Set	Supports Protocol Objective Number	Subgroups	Statistical Method	Covariates/ Strata	Missing Data
Response based on achieving the IGA of clear (0) or almost clear (1) (on a 5-point scale) at month 3	FAS, mFAS, PP	1	All	Percentage of patients with IGA score 0 or 1 at month 3 Chi-Square test respective Fisher's exact test for subgroups	None	Excluded
Response based on achieving the EASI-75 at month 3	FAS, mFAS, PP	2	All	Percentage of patients with 75% reduction from baseline in EASI at month 3 Chi-Square test respective Fisher's exact test for subgroups	None	Excluded
Response based on achieving the IGA of clear (0) or almost clear (1) (on a 5-point scale)	FAS, mFAS, PP	3	All	Percentage of patients with IGA score 0 or 1 irrespective of the point in time Chi-Square test respective Fisher's exact test for subgroups	None	Excluded
Response based on achieving the EASI-75	FAS, mFAS, PP	4	All	Percentage of patients with 75% reduction from baseline in EASI irrespective of the point in time Chi-Square test respective Fisher's exact test for subgroups	None	Excluded

Outcome **Analysis Set Supports Missing Data** Subgroups Statistical Method Covariates/ Strata Protocol **Objective** Number Response based on FAS, mFAS, PP All Percentage of patients None Excluded achieving the EASI-90 with 90% reduction from baseline in EASI irrespective of the 5 point in time Chi-Square test respective Fisher's exact test for subgroups Percentage of patients Response based on FAS, mFAS, PP Excluded All None achieving the IGA of with IGA score 0 or 1 clear (0) or almost clear and a reduction from (1) and a reduction from baseline of ≥ 2 points baseline of ≥2 points irrespective of the 6 point in time Chi-Square test respective Fisher's exact test for subgroups Percentage change of FAS, mFAS, PP (score at respective All None Excluded IGA compared to visit - score at baseline baseline)/score at 7 baseline*100 Mann-Whitney-U test for subgroups (score at respective Percentage change of FAS, mFAS, PP All None Excluded SCORAD compared to visit - score at baseline baseline)/score at baseline*100 Mann-Whitney-U test for subgroups Absolute EASI values FAS, mFAS, PP All Summary statistics (n, None Excluded mean, median, over time standard deviation, 9 minimum and maximum) of the score at each point in time

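### Four secondary response endpoints in the SAP have no defined time point and do not clearly carry over the protocol's by-visit assessment

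*SAP*

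**What the plan says.** Protocol 9.1.1 introduces the physician-assessed secondary endpoints with "Physician's global assessment of efficacy parameters (assessed at all visits [except for month 3 for a. and b". Items a and b are IGA 0/1 and EASI-75, whose month 3 values are the primary endpoints. EASI-90 and IGA 0/1 with a reduction of at least 2 points fall under the same heading without that exception.

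SAP 6.1 gives the operational definition of secondary EASI-75 as "Percentage of patients with 75% reduction from baseline in EASI irrespective of the point in time" and words EASI-90 and both IGA responses the same way. The four matching rows of SAP 8.2.3 repeat it, for example "Percentage of patients with IGA score 0 or 1 irrespective of the point in time". In the same EASI and IGA cells of 6.1, the score summaries are worded differently: "of the score at each point in time as well as the respective percentage change to baseline".

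No other text settles the meaning:
- SAP 8.2.2 only refers back to 6.1 and 6.3.
- The responder definitions in SAP Appendix 1 name no visit, and heading A1.2, meant for further endpoint definitions, has no text under it.
- SAP 8.1 plans frequencies for binary and ordinal variables but does not say by visit.
- SAP 9 places the table shells in a separate file, which was not available for this review.

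**The concern.** A response percentage needs a time point, or a rule for combining time points. Here the wording permits at least two results under one endpoint name: a percentage at each visit, or the percentage of patients who respond at any visit. Pooling all visits is a third possibility. Two programmers could follow the SAP and report different numbers.

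If the any-visit rate is produced, four things follow:
- It cannot be set beside the month 3 primary rate.
- It mixes month 3 back into IGA 0/1 and EASI-75, where the protocol leaves it out.
- It counts a transient response the same as one kept to month 12.
- It depends on documentation. Visits are optional (protocol 9.2.3.2), and each extra visit is another chance to be counted as a responder. Per-protocol patients are those who "completed all visits, irrespective of the time-window", whereas FAS patients need not have completed all visits. The two sets could therefore differ for this reason alone.

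SAP section 2 also promises, at the second interim analysis, "usage of abrocitinib and effectiveness at each available timepoint". A single any-visit figure would not deliver that for response; the by-visit score summaries meet it only in part.

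**Working it through.** The plan states no figure for these endpoints, so there is none to reproduce. The check has a textual part and an illustration of size.

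**Text side by side**

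| Endpoint | Protocol 9.1.1 | SAP 6.1 and 8.2.3 |
|---|---|---|
| IGA 0/1 | all visits except month 3 | no visit named |
| EASI-75 | all visits except month 3 | no visit named |
| EASI-90 | all visits | no visit named |
| IGA 0/1 and reduction of at least 2 points | all visits | no visit named |
| EASI and IGA scores | all visits | each time point |

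Two different time phrases inside the same cells suggest two different meanings, which favours the any-visit reading. Against this, SAP section 6 says that "the respective time windows for post-baseline visits are given in Table 2", and the table is loose about time elsewhere: the pruritus row reads "Percentage of patients achieving at least 4 points improvement of Pruritus NRS from baseline" with no time at all, and the DLQI response row is similar. The by-visit reading therefore remains possible.

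**Without assumptions**

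On complete data, every patient who responds at the best visit is also an any-visit responder, so

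any-visit rate ≥ max over visits of p_k.

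For one patient, or a fixed denominator, adding a documented visit can only leave the result unchanged or raise it. With missing data excluded (SAP 8.2.3) the denominator can grow too. One newly assessed non-responder moves 50/100 = 50.0% to 50/101 = 49.5%, so the overall rate can also fall.

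**Illustration (assumed rates and correlations)**

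Model: each patient has equicorrelated latent normal values with correlation ρ over the five post-baseline visits, all observed, and responds at visit k with probability p_k. Then

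any-visit rate = 1 − E_b{ ∏_k [1 − Φ((Φ⁻¹(p_k) − √ρ·b)/√(1−ρ))] }, with b standard normal.

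Assumed p = 40, 50, 45, 40, 35% at months 1, 3, 6, 9, 12. The peak is 50% and the pooled mean is (40+50+45+40+35)/5 = 42%.

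| | ρ = 0.5 | ρ = 0.7 | ρ = 0.9 |
|---|---|---|---|
| Any-visit rate | 77.1% | 69.0% | 58.2% |
| Excess over the 50% peak (points) | 27.1 | 19.0 | 8.2 |
| Any-visit rate without month 3 | 70.9% | 63.5% | 53.6% |
| Added by month 3 (points) | 6.2 | 5.5 | 4.6 |
| Any-visit responders not in response at month 12, 1 − 0.35/any | 54.6% | 49.3% | 39.9% |

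Effect of visit count alone, with p = 50% at every visit:

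| | ρ = 0.5 | ρ = 0.7 | ρ = 0.9 |
|---|---|---|---|
| Five documented visits | 83.3% | 75.7% | 64.7% |
| Three documented visits | 75.0% | 69.0% | 60.8% |
| Difference (points) | 8.3 | 6.7 | 4.0 |

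**The case against.** The best counter-argument is that the SAP means by-visit percentages. The primary rows just above tie the same responses to month 3, so the secondary wording may only say that they are no longer tied to it. SAP 6.1 counts all secondary endpoints as effectiveness endpoints, and section 2 promises effectiveness at each available time point for the second interim analysis. The unseen shells may already be laid out by visit. Protocol 9.7 also lets the SAP modify the protocol's plans and promises an amendment only for major changes to the primary endpoints.

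Much of this stands. The by-visit reading cannot be excluded, and an any-visit definition would break no stated rule. But these points show that the text supports two readings, which is the problem. If by-visit is meant, the correction only records it. If a change from the protocol is meant, it is not stated and has no denominator.

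It is also true that the size is assumed. In the same example the excess over the peak falls to about 4 points at ρ = 0.95 and 2 points at ρ = 0.98. If the visit rates were equal and responses perfectly correlated, it would be zero. Only the inequality is free of assumptions.

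Finally, the study is descriptive, EASI and IGA scores are summarised by visit, and under SAP 5.3 the per-protocol set is used only if it omits at least 10% of the mFAS. These points limit the consequence. In a descriptive study, though, the percentage is itself the result, and these rows also carry subgroup tests.

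**Conclusion.** The concern holds. Four secondary response endpoints have no single reproducible definition in the SAP, and the protocol's by-visit assessment, including the month 3 exception, is not clearly carried over. That the phrase is undefined is certain from the two documents. That any-visit response is meant is only the more natural reading, and the shells could overturn it.

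Under that reading the rate is at least the best single-visit rate on complete data. In the illustration it exceeds the best visit by 8 to 27 points for correlations of 0.9 to 0.5. This rests on assumed visit rates, equicorrelated latent responses and complete visits. The primary endpoints are unaffected. The point should be fixed before the final analysis.

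**What to change.** In SAP 6.1 and the four matching rows of 8.2.3, replace the undefined phrase with named visits:
- **IGA 0/1 and EASI-75:** months 1, 6, 9 and 12.
- **EASI-90 and IGA 0/1 with a reduction of at least 2 points:** months 1, 3, 6, 9 and 12.
- **All four:** report the number of patients assessed at each visit.

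Then check that the table shells agree.

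If an any-visit rate is also wanted, report it as a separately labelled summary. Give it a stated denominator, for example patients with a baseline and at least one post-baseline assessment, and the number of visits contributing. The pruritus NRS, peak pruritus NRS and DLQI response rows, which name no visit, could be dated in the same edit.

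The cost is SAP wording and, if the shells lack them, by-visit rows in existing tables. No new data are needed.

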5 ANALYSIS SETS/POPULATIONS

5.1 FULL ANALYSIS SET

The Full Analysis Set (FAS) consists of all patients with informed consent who met the eligibility criteria and received at least one dose of abrocitinib. This population will be used for all analyses except safety.

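### The at-least-4-point responder rates for Pruritus NRS, PP-NRS and DLQI include any patient whose baseline is too low to respond; report them among patients with a baseline of 4 or more, with the all-patient rate alongside

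*SAP*

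**What the plan says.** The protocol (9.1.1) lists one such endpoint among the patient-assessed secondary endpoints: "Response based on achieving at least 4 points improvement of Pruritus NRS from baseline". SAP 6.1 carries it over as "Percentage of patients achieving at least 4 points improvement of Pruritus NRS from baseline" and adds two more of the same form: "Percentage of patients achieving at least 4 points improvement of PP NRS from baseline" and "Percentage of patients achieving at least 4 points improvement of DLQI from baseline". The summary table in SAP 8.2.3 repeats all three, with chi-square or Fisher tests for every subgroup, no covariates, and missing data excluded.

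No analysis set adds a baseline-score condition. Of the FAS, SAP 5.1 says "This population will be used for all analyses except safety". The mFAS in SAP 5.3 covers eligible patients who "received at least one dose of abrocitinib and had at least one post-baseline visit". The per-protocol set adds only completion of all visits. A missing baseline removes a patient from change analyses (SAP 1.1), but a low baseline does not. SAP Appendix 1 has no denominator rule for these endpoints.

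The inclusion criteria (protocol 9.2.1) ask for a dermatologist's diagnosis of AD and eligibility under the product label. They set no minimum itch or DLQI score.

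**The concern.** Both itch scales run from 0 to 10. For DLQI, "The sum of scores ranges from 0 to 30". On a scale that cannot go below 0, a patient who starts at 0, 1, 2 or 3 cannot improve by 4 points. Such a patient adds to the denominator and can never add to the numerator, so the rate mixes how often treatment works with how many patients started too low to show it.

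Low baselines are not ruled out. Patients may restart abrocitinib after 28 days off it. The wash-out exclusions in protocol 9.2.2 cover only investigational drugs and abrocitinib, so a partly controlled patient coming from another approved systemic drug can enter.

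Two things are at stake. One is the level of three secondary responder rates. The other is the unadjusted subgroup tests: SAP section 4 says they are meant to generate hypotheses, and the rationale speaks of identifying predictors of response. If one medication-history class starts with less itch than another, a floor effect could be read as a predictor.

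**Working it through.** The plan gives no expected responder rate, baseline distribution or formal sample size calculation, so there is no figure of its own to reproduce. The check is algebra on the written definition, with assumed values shown as a range.

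**Inputs from the documents.** The threshold is 4 points (SAP 6.1) and the scale floor is 0 on all three instruments (SAP 6.1, questionnaire table). The baseline-score conditions are none (SAP 5.1, 5.3, 8.2.3, Appendix 1; protocol 9.2.1). Planned enrolment is at least 750 (protocol 9.5).

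**Assumed inputs.** q is the share of analysed patients with baseline below 4. p is the responder rate among those with baseline of at least 4. I follow the rule in SAP 8.2.3 that missing values are excluded.

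**Who can respond.** The largest possible improvement from baseline b is b. So b = 0, 1, 2 or 3 can never reach 4, and b = 4 just can.

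**Effect on the rate.** Reported rate = p × (1 − q) + 0 × q = p × (1 − q). The loss is p × q.

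| q | Rate if p = 40% | Rate if p = 60% | Loss if p = 60% |
|---|---|---|---|
| 2% | 39.2% | 58.8% | 1.2 points |
| 5% | 38.0% | 57.0% | 3.0 points |
| 10% | 36.0% | 54.0% | 6.0 points |
| 20% | 32.0% | 48.0% | 12.0 points |

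If 750 patients were analysed, q = 2%, 10% and 20% would be 15, 75 and 150 patients who cannot respond.

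**Effect on a subgroup comparison.** With the same p in classes A and B, the artificial gap is p × (qB − qA). At p = 60%:

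- q of 10% in both classes: gap 0.
- q of 5% and 10%: 0.60 × 0.05 = 3 points.
- q of 5% and 15%: 0.60 × 0.10 = 6 points. The chance of a nominally significant result (two-sided 0.05, equal classes) is about 9%, 13% or 22% with 50, 100 or 200 per class.
- q of 5% and 25%: 0.60 × 0.20 = 12 points. The chance is about 22%, 40% or 67% at the same sizes.

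**What restriction achieves.** Among patients with baseline of at least 4 the rate is p. The gap above is then 0 if p is the same in both classes. It does not remove every link with baseline. Suppose each patient improves by 60% of the starting score: baselines of 4, 5 and 6 fall by 2.4, 3.0 and 3.6 and miss the threshold, while 7 falls by 4.2 and meets it. A class with milder itch would still look somewhat worse.

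**Which subgroups.** Of the five in SAP 5.4, dose sequence, switching, abrocitinib response and EASI-90 response depend on what happens after baseline. Only medication history is fixed at baseline. The other four carry confounding by outcome that no denominator rule would cure.

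**The case against.** The denominator is inferred. The SAP states a percentage of patients and does not spell out who is counted. SAP section 9 leaves the table shells to a separate file that is not among the documents, and a restriction could appear there. This stands as a limit, but the SAP text should carry the rule.

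The study concerns moderate to severe AD, in which the protocol calls itch the predominant symptom, so few patients may start below 4. This also stands. A reader might infer that the rates understate response materially and that subgroup comparisons are distorted as a matter of course. The documents support neither: they give no q, no passage says that restarting patients have mild itch, and with equal q there is no artificial gap.

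A reader might also extend the criticism to the endpoints that count patients with a score of 1 or less, because someone already there at baseline counts without any change. Those endpoints describe a disease state at a visit, and all patients are a legitimate denominator for that. The primary IGA 0/1 endpoint has the same form.

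Finally, these are secondary endpoints in a descriptive single-arm study, the tests are declared exploratory, and the SAP already tabulates baseline summaries and percentage changes for all three scales. The baseline minimum would show whether anyone starts too low, but not how many or in which class. The all-patient rate is a valid description of practice, which is why it should be kept.

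**Conclusion.** The point holds in a limited form. As the SAP is written, any patient with a baseline of 0 to 3 is a certain non-responder on the three at-least-4-point endpoints, and the reported rate is p × (1 − q). The size depends wholly on q, which the documents do not give. With p assumed to be 60%, the loss ranges from a negligible 1.2 points at q = 2% to 12 points at q = 20%. A false subgroup difference needs unequal q between classes; medication history is where that is most relevant. The 12-point gap and the 22% to 67% chances above illustrate a 5% versus 25% imbalance that no passage documents. The primary IGA and EASI-75 analyses are untouched. The change is worth making because it costs almost nothing and makes these rates easier to interpret.

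**What to change.** In SAP 6.1 and 8.2.3, for Pruritus NRS, PP-NRS and DLQI:

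- Report each at-least-4-point rate, and run its subgroup test, among patients with a baseline score of at least 4.
- Show the number excluded for a baseline below 4, overall and in each subgroup class.
- Keep the all-patient rate alongside.
- Note in the SAP that some dependence on baseline severity remains among patients at 4 or above.

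Leave the endpoints for a score of 1 or less as all-patient descriptions, and print next to them the proportion already at 1 or less at baseline.

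The cost is SAP wording, one extra line per table and a slightly smaller denominator. No new data are needed. Settling the denominator before database lock avoids choosing it after the results are known.
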